Objectives	Analysis and reporting:	Aug 2023 – Dec 2023 Outcome Measures
Objectives Main outcome measures relati	ng to fossibility (no prim	
Feasibility of recruitment		Ability to achieve recruitment rate of 5-6 patients per month (number screened, consented, and randomised will be logged; reasons for non- consent or withdrawal will be recorded).
Feasibility of delivering the study intervention (Venner PneuX) including device-related complications		Issues with delivering intervention will be recorded including protocol deviation and device-related complications.
Acceptability of study interventions and sampling amongst staff.		Short qualitative interviews and/or surveys will be carried out with study staff to determine acceptability of study interventions, including barriers and facilitators to delivering the study intervention.
Feasibility of pepsin sampling procedure using Peptest		Issues with pepsin sampling will be recorded (including repeated or failed pepsin sampling, problems with logistics)
Establish the rate of positive pepsin samples in both arms of the study using Peptest		Number of pepsin-positive samples
Establish the mean volume of sub-glottic aspirates using the control and intervention groups		Volume of sub-glottic secretions
Secondary outcomes		
Establish the rate of tracheobronchial colonization		Tracheobronchial colonization (no. colony forming units/ml)
Establish rates of Ventilator Associated Pneumonia (VAP)		No. patients with VAP diagnosis using CPIS scoring criteria

Assess mean time spent on the ventilator		Duration of mechanical ventilation in ICU (from time/date of intubation to time/date of extubation)
Assess both hospital and ICU ler	ngth of stay (LOS)	Length of stay in ICU and length of stay in hospital
Assess in-hospital mortality rate	es/ All-cause mortality	Number of patients who die in hospital
Assess cuff pressure		Cuff pressures in both arms of study (measured 12 hourly)
Intervention	Venner PneuX [™] Endotracheal Tube (ETT) (manufacturer by Venner Medical; distributed by Qualitech Healthcare)	
Statistical Methodology and	Descriptive statistics of numerical outcome data including measurements	
Analysis	of precision will be reported. The study is to evaluate if a larger, adequately powered randomised controlled study can be conducted to compare outcomes between groups.	

Funding and support in kind

Funder	Financial and non-financial support given
Chief Investigator (Pathway to Portfolio grant, plus PI	Financial

1.1. The clinical problem

Ventilator-associated pneumonia (VAP) is the most frequent nosocomial infection among patients requiring intubation and mechanical ventilation in an intensive care unit (Wicky et al. 2022). It is defined as a pneumonia that develops 48 hours or more after intubation with an endotracheal or tracheostomy tube. VAP is associated with an increase in length of ventilator time, length of critical care, hospital stay, morbidity, mortality and cost (Bekaert et al. 2011; Melsen et al. 2013; Safdar et al. 2005; Nseir et al. 2005; Rello et al. 1996). However there remains no gold standard for diagnosing VAP in mechanically ventilated patients, and definite diagnosis relies upon clinical signs, symptoms, radiological and microbiological confirmation. Consequently, there is an absence of reliable epidemiological data on the incidence and mortality of VAP in the UK, but estimates for critical care environments range from 10-20%; causing an increase in hospital length of stay by an average of 4-9 days (Chastre and Fagon 2002; Morris et al. 2011). Internationally, rates of VAP also vary widely in the literature from 9.3% (Rello et al. 2002) to 20.3% in a recent meta-analysis of 6284 patient's in 24 trials (Melsen et al. 2013). In England alone, between 3,000 and 6,000 people die from VAP each year according to NHS England (NHS England, 2016).

1.2. Pathogenesis of VAP

Patients that require mechanical ventilation to help them breathe are fitted with a conventional endotracheal tube (ETT) into their mouth, or through an incision in their neck (tracheostomy). The pathogenesis of VAP is linked to the presence of the ETT in the oropharynx. This results in a loss of both the natural defence mechanisms of the cough reflex and natural anatomical barriers (i.e. the glottis and larynx); it is further compounded by the placement of foreign material within the respiratory tract (Young and Doyle 2012). As a result, oropharyngeal secretions become excessive, and combined with gastric contents refluxed into the oropharynx, causes a pool of secretions above the ETT cuff. Microfolds developing in the inelastic inflated cuff can allow the microaspiration of these bacteria-laden subglottic secretions past the cuff and into the lower respiratory tract. This is the first route of entry of bacteria into the lower respiratory tract in patients receiving mechanical ventilation, and is diagnosed in 50-75% of these patients (Nseir et al. 2011; Metheny 2006). High bacterial load combined with chemical and enzymatic injury from gastric secretions can overwhelm pulmonary defences and become a key factor in the pathogenesis of VAP (Metheny 2006). This microaspiration of contaminated secretions is sine qua non of VAP, and remains a limitation of the existing standard ETTs used currently. As a result, this has prompted a considerable interest in the development of an ETT that can retain adequate cuff pressure against the tracheal wall, thus preventing microaspiration (Zolfaghari and Wyncoll 2011; Metheny 2006).

1.3. Standard endotracheal tubes

Conventionally, ETTs have high-volume, low pressure (HVLP) cuffs and when inflated manually, have a diameter larger than the adult trachea which is designed to prevent tracheal mucosal injury by allowing the pressure within the cuff to be equal to the tracheal wall pressure (Young et al. 2006). Therefore, the cuff is only partially inflated and the excess material within the cuff causes material folds and channels to develop. These channels facilitate aspiration of subglottic secretions, and contribute to an increase in VAP.

The pooling of subglottic secretions requires continuous suction with standard ETTs, which can produce ischaemic injury to tracheal mucosa, and so intermittent drainage through ports in the ETT is more commonly adopted nowadays. However, these ports can become blocked by suctioned tracheal mucosa.

1.4. The Venner PneuX system

The Venner PneuX is a single use ETT intended for patients undergoing tracheal intubation during routine anaesthesia or over extended periods (not more than 30 days), and for the evacuation or drainage of secretions from the subglottic space. The system comprises three components: an ETT tube, a tracheal seal monitor, and a 2 m extension tube. The PneuX device has two unique features; a boat tip with murphy eye to aid the passage of the ETT through the larynx to the trachea to reduce the risk of airway occlusion, and an integrated bite block to resist damage from biting. In addition, the PneuX device also combines common features of ETTs designed to prevent the microaspiration of secretions; an electronic automated tracheal seal monitor to maintain the intracuff/tracheal wall seal pressure; and a low-volume, low-pressure (LVLP) cuff made from a soft silicone material. The cuff inflates automatically to a 30 cm H₂0 pressure, uniformly and circumferentially, providing a continuously watertight seal between the cuff and tracheal mucosa, and thus preventing the aspiration of air and/or fluid around the ETT. This pressure reduces the mucosal injury caused by HVLP cuffs whilst preventing the formation of micro-folds. With such a tight seal, PneuX is said to be safer in allowing subglottic secretions to build up above the cuff and perform intermittent subglottic secretion drainage (Doyle 2011).

To try and circumvent the issue of subglottic port blockage, the PneuX device has three small circumferential subglottic secretion drainage and irrigation ports above the proximal end of the cuff. These ports enable intermittent subglottic drainage and irrigation to be done through the two unoccluded ports; should one of them become obstructed by suctioned tracheal mucosa. This involves the use of a cleaning fluid (usually saline) to wash out the space above the cuff and oropharyngeal space.

In a randomised controlled trial, patients using PneuX for ventilation had a lower incidence of colonization than those using standard ETT, however there was no difference in the type of bacterial colonization (Senanayake et al. 2017).

1.5. Clinical and cost-effectiveness by NICE

NICE reviewed the clinical and cost effectiveness of PneuX in 2020 (MTG48 PneuX to prevent ventilatorassociated pneumonia). The clinical evidence indicated that PneuX decreases VAP incidence compared with endotracheal tubes without subglottic drainage, but does not reduce ICU length of stay or mortality. The clinical evidence comprised 3 studies including a total of 341 adults in cardiac or general intensive care. Only one of these studies was a randomised controlled trial comparing PneuX with a standard endotracheal tube (ETT) without drainage in high-risk patients (over 70 or with a left ventricular ejection from or under 50%, or both) (Gopal et al. 2015). Gopal demonstrated a significantly lower incidence of VAP in the PneuX groups than the standard care group (ETT without subglottic secretion drainage): 10.8% vs. 21% (P=0.03) with a relative risk of 0.52. There was no significant difference in length of ICU stay (PneuX: 2 days, Standard care: 1.5 days [p =0.2]), and in-hospital mortality (PneuX survival rate: 98% Vs. 99% for standard endotracheal tube [p = 0.2].

The other studies were non-comparative and are more generalisable to people needing ventilation with a wider range of health conditions. (Smith, Khan, and Gratrix 2014; Nct, Shenfeld, and Jacob 2007; Hodd and

Young 2009; Doyle 2011). The rates of VAP were very low in these studies, however a lack of a control group and differing definitions for diagnosing VAP across the studies makes it difficult to draw any meaningful conclusions about the efficacy of PneuX in the treatment of VAP.

In a meta-analysis of 20 RCTs, including 3544 patients, subglottic secretion drainage (including devices other than PneuX) was associated with a significant reduction of VAP incidence compared with non-subglottic drainage (in four high quality trials; the relative risk was 0.54 (95% CI 0.40-0.74, *p*<0.00001) (Mao et al. 2016).

NICE also carried out a review of the economic evidence in 2020. The company model cost analysis (by Venner) found that PneuX was cost saving when compared to endotracheal tubes without subglottic secretion drainage. The results indicated a cost saving of £738 per patient after cardiac surgery when PneuX is used instead of an ETT without subglottic drainage. This saving was from an absolute reduction in the risk of VAP of around 10% for PneuX and the associated reduction in resource consumption based on avoided costs of around £9,000 per VAP prevented. The cost of a PneuX device was £150 vs. £5 for ETT without drainage, which is a modest cost compared to the above cost of treating VAP as cost savings for PneuX are driven by a reduction in VAP, which may cause costly increases in length of ICU stay.

1.5.1. NICE recommendations

NICE produced a series of research recommendations during its review of the PneuX device in 2020. They are as follows:

- PneuX shows promise for preventing ventilator-associated pneumonia in adults. However, there is currently not enough good-quality evidence to support the case for routine adoption in the NHS.
- Research is recommended to address uncertainties about the clinical benefits of using PneuX. This research should:
 - assess whether PneuX reduces the incidence of ventilator-associated pneumonia in all people needing ventilation
 - compare PneuX with current NHS clinical practice, that is, the use of endotracheal tubes with subglottic drainage
 - \circ ~ evaluate <code>PneuX</code> within the care bundle for ventilator-associated pneumonia prevention
 - \circ $\,$ be clear about the criteria used to diagnose ventilator-associated pneumonia in the study.

1.6. Pepsin as a biomarker of microaspiration

Several biomarkers of microaspiration have been used in the literature concerning VAPs, but it is pepsin that is the most validated as an accurate marker by several animal and human studies. Pepsin is synthesised from its inactive precursor pepsinogen, and is secreted by the chief cells in the stomach following vagal or gastrin stimulation (Garland et al. 2014). As pepsin is not normally present in the respiratory tract, its presence is a reliable marker of gastric-to-pulmonary aspiration, and as a surrogate to evaluate the efficacy of an endotracheal tube in preventing VAP (Dewavrin et al. 2014). Unlike other biomarkers of aspiration, the analysis of pepsin from tracheal secretions is rapid, easy to perform and cheap, and is therefore the biomarker of choice used in this feasibility study (Metheny 2006; Metheny et al. 2004; Bohman et al. 2018; Jaillette et al. 2013).

1.7. Pepsin analysis

To detect pepsin in the subglottic aspirate samples in this feasibility study, Peptest (RD Biomed) will be used. Peptest is a CE marked, non-invasive, single-use, *in-vitro* diagnostic medical device for detecting pepsin in saliva or sputum. The device is a lateral flow device containing two types of unique monoclonal antibodies against pepsin on a nitrocellulose membrane in a plastic case. On application of a sample, one of the antibodies tagged with a colorimetric marker becomes soluble and the second antibody is immobilised at the 'T band' line in the viewing window. Any pepsin in the sample is bound at the test line by the two antibodies, and if present at a concentration of 16 ng/ml or more, a coloured line is seen within 15 minutes, giving a qualitative result. Furthermore, the intensity of the T band is directly proportional to the pepsin quantity and can be quantified using a PepCube reader (RD Biomed). This is a portable electronic handheld lateral flow device reader using colorimetric analysis based on reflectance measurements to capture the optical density of the 'T band', giving a semi-quantitative level down to a detection limit of 25 ng/ml according to the manufacturer. There is an absence of agreed normal physiological range for pepsin levels in saliva, however published studies have used different pepsin concentrations ranging from 16 ng/ml to 25 ng/ml as a cut-off value to indicate a clinically significant concentration of pepsin in saliva – both of which are detectable by the Peptest lateral flow device.

2. Rationale

NICE have produced guidance on PneuX to prevent VAP. The committee stated that PneuX shows promise for preventing VAP in adults, however there is currently not enough good-quality clinical evidence to support the case for routine adoption in the NHS. NICE has therefore recommended that further research should be done to address several outstanding uncertainties surrounding the technology and its place in clinical practice.

We propose a full randomised controlled trial (RCT) to address the question of whether the PneuX device reduces the microaspiration of pepsin, and the impact of several secondary outcomes, including VAP rate. Before a full-scale RCT can be done, **we propose this feasibility study using 50 patients to be undertaken**. This will help to identify the intervention fidelity – the extent of which the intervention can be delivered as intended and will help to reveal any problems or obstacles related to implementation of the study. Any problems identified can then be remedied to ensure methodological rigour and scientific validity in the full-scale RCT. The feasibility study will establish the acceptability of the randomisation procedure by clinicians. Similarly, the willingness of patients to participate in the study and the appetite for clinicians to recruit participants will need to be ascertained.

2.1. Assessment and management of risk

The Venner PneuX[™] Endotracheal Tube (ETT) single use device, is intended for patients undergoing tracheal intubation during routine anaesthesia or over extended periods (not more than 30 days) and for the evacuation or drainage of secretions from the subglottic space. The PneuX ETT is a Class IIa CE marked medical device. In this study the device will be used as per its intended purpose, as described in the Instructions for Use (IFU). As such the study is on a CE marked medical device used as per its intended purpose (described in the IFU). As such this trial is categorised as: Type A = No higher than the risk of standard medical care.

3. Objectives and outcome measures/endpoints

3.1. Hypothesis

This is a feasibility RCT and as such will not be testing a hypothesis.

3.2. Aims

The study aims to assess the feasibility of conducting an RCT to compare the PneuX ETT with standard care in hospitalised patients requiring mechanical ventilation. The study will investigate several feasibility measures including recruitment, delivery of the intervention (including device-related adverse events), acceptability and adherence to the intervention and sampling, use of Peptest to measure microaspiration events, rate of pepsin positive samples, volume of sub-glottic aspirate, rate of VAP, length of ICU and hospital stay, demonstrate the validity of study documentation and provide preliminary data for 50 patients. The data will inform the pilot and main phase of the study.

3.3. Main objectives

- 1. Feasibility of recruitment
- 2. Feasibility of delivering the study intervention (Venner PneuX) including device-related complications
- 3. Acceptability of study interventions and sampling amongst staff
- 4. Feasibility of pepsin sampling procedure for use in Peptest
- 5. Establish the rate of positive pepsin samples in both arms of the study using Peptest
- 6. Establish the mean volume of sub-glottic aspirates using the control and intervention groups

3.4. Secondary objectives

- 1. Establish the rate of tracheobronchial colonization
- 2. Assess antibiotic usage and duration
- 3. Establish rates of Ventilator Associated Pneumonia (VAP)
- 4. Assess mean time spent on the ventilator
- 5. Assess both hospital and ICU length of stay (LOS)
- 6. Assess in-hospital mortality rates/ All-cause mortality
- 7. Assess compliance with measuring and documenting cuff pressure

3.5. Table of endpoints/outcomes

Objectives	Outcome Measures	Timepoint(s) of evaluation of this outcome measure (if applicable)
Main outcome measures relating to fea	asibility (no primary)	
Feasibility of recruitment	Ability to achieve recruitment rate of 5-6 patients per month (number screened, consented, and randomised will be logged; reasons for non-consent or withdrawal will be recorded)	Continuously over duration of study
Feasibility of delivering the study intervention (Venner PneuX) including device-related complications	Issues with delivering intervention will be recorded including protocol deviation and device-related complications.	Continuously over duration of study

Acceptability of study interventions and sampling amongst staff.	Short qualitative interviews and/or surveys will be carries out with study staff to determine acceptability of study interventions, including barriers and facilitators to delivering the study intervention.	Staff will be interviewed or surveyed at study end		
Feasibility of pepsin sampling procedure for use in Peptest	Issues with pepsin sampling will be recorded (including repeated or failed pepsin sampling, problems with logistics)	Continuously over duration of study		
Establish the rate of positive pepsin samples in both arms of the study using Peptest	Number of pepsin-positive samples	Continuously over duration of study		
Establish the mean volume of sub- glottic aspirates using the control and intervention groups	Volume of sub-glottic secretions	Continuously over duration of study		
Secondary outcomes		•		
Establish the rate of tracheobronchial colonization	Tracheobronchial colonization (no. colony forming units/ml)	Samples taken on day 3 and day 7 for cultures		
Antibiotic use	Antibiotic prescribed, indication for use, number of days administered	Continuously over duration of study		
Establish rates of Ventilator Associated Pneumonia (VAP)	Number of patients with VAP diagnosis. Clinical Pulmonary Infection Score (CPIS) used to predict VAP. CPIS >6 will be used to define confirmation of VAP.	Measured daily after 48 hours of intubation		
Assess mean time spent on the ventilator	Days spent with mechanical ventilation in ICU (from time/date of intubation to time/date of extubation or 28 days)	Continuously over duration of study		
Assess both hospital and ICU length of stay (LOS)	Length of stay in ICU and length of stay in hospital measured in days from ventilation	Continuously over duration of study		
Assess in-hospital mortality rates/ All- cause mortality	Number of patients who die in hospital	Death defined up to day 28		
Assess compliance with measuring and documenting cuff pressure	Documentation of cuff pressures in both arms of study. Cuff pressure in standard care will be measured every 12 hours. Assessment of intervention arm will have documentation that pressure has been maintained hourly either via the continual cuff pressure monitor or manually.	Duration that patient is intubated and mechanically ventilated		

4. Trial design

This is a single centre, open-label, feasibility randomised controlled trial. Patients will be randomised in equal proportions into one of 2 arms: to be intubated using a Venner PneuX Endotracheal Tube (ETT) or using the standard tube, e.g. Covidien Taperguard. For this feasibility study, a total of 50 patients will be randomised into

Sponsor reference: 21/NOV/8290

two groups (25 in each). All patients will be recruited at a single site (University Hospital of Wales, part of Cardiff & Vale UHB).

This feasibility study will assess various aspects relating to the feasibility of a larger RCT which would investigate whether the PneuX ETT reduces the incidence of microaspiration events in ventilated patients. The feasibility study will aim to highlight the most appropriate outcomes to be measured in a main RCT, particularly looking at the role of Pepsin detection in subglottic-aspirate samples.

Coordination of the trial will be carried out by a trial manager from Cedar, Cardiff & Vale UHB.

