6.5. Trial assessments

Study assessment are summarised as follows:

Task	Screening	Randomisation (day 0)	Daily (day 1-7)	Follow-up (day 28)
Assess eligibility to enter study (record reason if not eligible)	x			
Demographics and eligibility checklist		Х		
Record date and time of randomisation (or reason if not randomised)		x		

Intubation using allocated endotracheal	X		
tube	x		
Admission to ICU			
Intubation details and device	X		
measurement			
ICU admission details and reason	×		
Quantity of aspirate and pepsin sampling for subglottic aspirate	X	X (every 24h)	
Quantity of aspirate and pepsin sampling	X	X (every 24h)	
for tracheal aspirate			
Send sample of aspirate for cultures		X (Day 3 + 7)*	
Document compliance with measuring	X	X	
and documenting cuff pressure			
Document antibiotic use		X	
Document VAP		X	
Duration of ICU LOS			Х
Duration of ventilation			Х
In hospital death			Х
Consent	X		
Adverse Reactions/Safety Reporting	X		
Protocol violations	Х		

*Or as clinically indicated

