6.6. Long term follow-up assessments

Information required regarding time ventilated, hospital LOS, in hospital death will be deemed long term follow up if these events exceed the 7-day study duration. All necessary information will be collected if hospital discharge is achieved within this stated 28-day period. No data is required following discharge.

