6.7. Withdrawal criteria

Each participant has the right to withdraw from the study at any time. In addition, the CI may withdraw a participant from the study at any time if the CI considers it necessary for any reason including:

- Ineligibility (either arising during the study or if, during the study, previously unknown issues come to light which would make the participant ineligible)
- Significant protocol deviation as decided by the CI
- Significant non-compliance with treatment regimen or study requirements
- Withdrawal of consent by the patient or consultee (patients' study data up to the point of withdrawal will be kept).

Daily data collection will cease if:

- The patient has been extubated in the first 24 hours following intubation
- Planned extubation (the patient has improved, or the tube required changing for clinical reasons)
- Un-planned extubation (accidental removal of the tube)
- The patient has died with the tracheal tube still in place
- The patient has had a tracheostomy.

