10.1. Data handling and record keeping

The PI and critical care research team will collect all clinical data. The data will be collected in a timely manner and be extracted from and consistent with the relevant source data. Each participant will be allocated a unique Participant Study Number at trial entry, and this will be used to identify him or her on the CRF for the duration of the trial. Data will be collected from the time of trial entry until hospital discharge. Trial data will be collected from the source data using a paper case report form (CRF) and then entered onto a secure electronic database (REDCap). The electronic database will be secured by appropriate access control and password protection.

Cedar will undertake a short survey or interview with staff involved in the study to collect data on the acceptability of the study procedures and to identify barriers and facilitators.

All paper and electronic documents will be stored securely at UHW (paper) or on Cardiff & Vale UHB servers (electronic) and only accessible by the critical care research team and authorised personnel. No patient identifiable data (PID) will be transferred outside of Cardiff & Vale UHB. Paper CRFs will be kept at the study site during the study period and when completed the CRFs will be signed-off by the study PI/CI or designee. Completed and signed-off CRFs will be transferred to Cedar (in person) as each patient completes the study period. Appropriate checks will be made to enable cross validation against the original source data and ensure accurate data entry. The database will be stored on Cedar's secure server (part of Cardiff and Value UHB server) which is backed-up every 24 hours. Data queries will be raised by Cedar (Cardiff and Vale UHB). Where clarification from site staff is required for data validations or missing data, site staff will respond to data queries ensuring that amendments are made as required.

SPSS will be used for data analysis.

Cedar will undertake source data verification for 100% of CRFs. This will require Cedar to access personal identifiable data in the study recruitment and in patients' medical notes. Study participants will provide explicit consent to the use of identifiable data for the purposes of the study.

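### The protocol gives conflicting windows for recording antibiotic use; if the schedule is followed, course duration is cut at day 7 or extubation, whichever comes first

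*Protocol*

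**What the plan says.** The objective in section 3.4 is "Assess antibiotic usage and duration". The outcome table in 3.5 measures it as "Antibiotic prescribed, indication for use, number of days administered", with the timepoint "Continuously over duration of study". Section 10.1 states in general terms: "Data will be collected from the time of trial entry until hospital discharge".

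Other sections are narrower:

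- **6.5 (schedule).** The row "Document antibiotic use" has one mark, in the daily column for days 1-7. It has none at day 0 or day 28. ICU stay, duration of ventilation and in-hospital death are marked at day 28.
- **6.7.** A list headed "Daily data collection will cease if" includes unplanned extubation, tracheostomy, death with the tube in place, and "Planned extubation (the patient has improved, or the tube required changing for clinical reasons").
- **6.6.** Time ventilated, hospital stay and in-hospital death "will be deemed long term follow up if these events exceed the 7-day study duration". Antibiotics are not in that list.
- **6.4.** The baseline items do not include current antibiotics.

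Antibiotic use is not mentioned in the secondary outcomes of the Trial summary, in 6.5.2 or in 9.3, so none of these settles the window.

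**The concern.** A count of days administered measures duration only if observation lasts until the course ends. Under the schedule, observation ends at day 7 or when the tube comes out. Section 6.5.2 has VAP arising only after 48 hours, and the Trial summary gives a typical tube time of 4-7 days. A course started for VAP therefore begins partway through a short window. The recorded count would be biased low and tied to when the patient was extubated.

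There is a second gap at the other end. Patients come from the emergency department, the wards and level 2 care (4.1), so some may already be on antibiotics when randomised. No listed baseline item captures this, and the outcome in 3.5 names no start date.

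The study is meant to inform the next phase (3.2) and to point to suitable outcomes for the main trial (section 4). Durations cut short in this way would be a poor guide for that. Two people reading the protocol could also collect different data for the same patient.

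**Working it through.** The protocol gives no figure for antibiotic duration, so there is none to reproduce. The check has two parts.

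**1. Which window applies?**

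| Place | Window implied for antibiotics |
|---|---|
| 3.5 | Continuous over the study; length not defined in the row |
| 10.1 | Trial entry to hospital discharge (general statement; antibiotics not named) |
| 6.5 | Days 1-7 |
| 6.7 | Daily items end at extubation, tracheostomy or death with the tube in place |
| 6.6 | Antibiotics not carried past day 7 |

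The wording in 3.5 does not decide it. Section 6.6 treats the study duration as 7 days, which would give the same cap as the schedule. Yet 3.5 uses the same phrase for time on the ventilator, measured there up to 28 days, and for hospital stay. The windows conflict.

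**2. What does the schedule reading cost?**

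Inputs:

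- The last scheduled daily record is day 7 (6.5).
- E is the last day with the tube in place; the typical range is 4-7 days (Trial summary).
- s is the day the course starts. For VAP the earliest is taken as day 3, from the 48-hour rule in 6.5.2.
- L is the course length. The documents do not give it, so it is assumed and varied from 5 to 14 days. This illustrates the range and implies nothing about treatment.

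Recordable days = max(0, min(7, E) - s + 1), and never more than L.

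Tube in place to day 7 or later:

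- s = 3: 7 - 3 + 1 = 5 days
- s = 5: 7 - 5 + 1 = 3 days
- s = 7: 7 - 7 + 1 = 1 day

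Share of the course recorded (recordable days divided by L):

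| Assumed L | Start day 3 | Start day 5 | Start day 7 |
|---|---|---|---|
| 5 days | 5/5 = 100% | 3/5 = 60% | 1/5 = 20% |
| 7 days | 5/7 = 71% | 3/7 = 43% | 1/7 = 14% |
| 10 days | 5/10 = 50% | 3/10 = 30% | 1/10 = 10% |
| 14 days | 5/14 = 36% | 3/14 = 21% | 1/14 = 7% |

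Earlier extubation shortens this further. With E = 4 and s = 3 the maximum is 4 - 3 + 1 = 2 days. With E = 5 and s = 4 it is 5 - 4 + 1 = 2 days.

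With a window to day 28, the latest start that is fully captured is day 28 - L + 1. That is day 24, 22, 19 or 15 for L = 5, 7, 10 or 14, provided the patient is still in hospital. Every start from day 3 to day 7 is then captured in full.

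**The case against.** The best defence is that the narrow window is not established. On the wording of 10.1, and on one reading of 3.5, nothing is lost before discharge. The schedule grid is also an imperfect guide. Its safety-reporting row shows a single mark as the table was extracted, although 8.4 requires serious adverse events to be recorded until 28 days after trial treatment ends. Section 6.7 does not name antibiotics or forbid later abstraction, and the medical notes and electronic records are the source data (6.4). Indication is recorded, which helps separate treatment of the admitting illness from treatment of VAP. The case report form is not shown and may hold dates.

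Most of this stands, and it limits the point to a contradiction with a conditional consequence. It does not remove it. The schedule is the place that assigns antibiotics to specific days, and 6.6 leaves them out of what continues. The protocol does not require start or stop dates. Indication does not supply the length of a course already running.

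Two stronger inferences are tempting. One is that the objective cannot be answered at all. The documents do not support that: agent, indication and antibiotic days while intubated within days 1-7 can be described even on the narrowest reading. The other is that truncation would distort a comparison of the arms. Section 9.3 rules out between-group comparisons, so no planned analysis is affected in that way.

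**Conclusion.** The point holds as an inconsistency: 3.5 and 10.1 support a wider window than 6.5, 6.6 and 6.7, and nothing else in the protocol resolves it. If the schedule is followed, full course duration is not obtained for most VAP courses in the range examined. The recordable maximum is 5, 3 or 1 days for starts on day 3, 5 or 7, and less with extubation before day 7. The percentages depend on the assumed course length. A 5-day course from day 3 with the tube in to day 7 is fully captured. Under the wider window there is no truncation before discharge, but courses running at randomisation would still not be a listed baseline item. The consequence is for descriptive durations carried into the next study's design, not for any test in this one.

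**What to change.** State one window for antibiotic use in 3.5, 6.5 and 6.6, and make clear that the stop rule in 6.7 does not end it.

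At the day-28 record check already made for ICU stay, ventilation and death, abstract the agent, indication, start date and stop date of every course active from randomisation to day 28 or discharge, whichever is first, regardless of extubation. Flag courses already running at randomisation so that they can be reported separately from those started afterwards.

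If the sponsor prefers to keep the schedule as it is, rename the outcome as antibiotic days while intubated, days 1-7, and reword objective 2 to match.

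The first option costs a few minutes of record abstraction per patient and a small change to the case report form, with no added visit or procedure. The second costs only wording, but gives up full course duration.
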